- 5) Patient engagement with their health: Patient Activation Measure (PAM-13) aims to understand the knowledge, beliefs and skills required by people to enable them to manage their long-term conditions [13]. It has been successfully used in African populations [14]. Our previous research found that patient activation increases with remote consulting [4]. Also that the PAM-13 [12] has face and content validity for assessing the impact of remote consulting.
- 6) Patient safety is assessed by counting the number of investigations processed by the facility monthly and matching these to the patient’s consultation type. An increase may indicate a higher safety threshold when the person cannot be examined. A decrease may indicate missed health needs. The meaning and impacts of changes in this indicator will be explored in the process evaluation.

Evidence from the secondary outcomes will be explored in the process evaluation.

Sample size

The trials in Nigeria and Tanzania will take place independently, but with identical designs. We plan to recruit 20 clusters in each country for the trial and we expect there to be an average of 100 active eligible patients at any one time in each cluster. We describe each of these active patients in each cluster as an open cohort- patients will leave the cohort if they are not seen for >5 months and newly diagnosed patients meeting the eligibility criteria can join the cohort. The trial has both non-inferiority and superiority inferential goals: we hypothesise the intervention will increase the remote consultation but not affect consultation trust, for example. We therefore opt to determine “minimum detectable effect” sizes rather than power to indicate the precision of the trial and the likely sizes of effect for which we can provide strong evidence of superiority or non-inferiority. Our calculations are based on the statistical models reported below and a power of 80%, a type I error rate of 5%, an ICC of 0.05, and a CAC of 0.8. The assumptions about each outcome and minimum detectable effect sizes are reported in the Table below.

| Outcome | Baseline assumed | Denominator or population | Treatment effect | Lower minimum | Upper minimum |
|----------------|-------------------------|----------------------------------|-------------------------|----------------------|----------------------|

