|----------------|-------------------------|----------------------------------|-------------------------|----------------------|----------------------|

| | | | | detectable effect | detectable effect |
|--|--|-----------------------------|----------------------|--------------------------|--------------------------|
| Face to face consultation/prescription rate | 0.25 consults/prescriptions per person-month | All active patients (n=100) | Incidence rate ratio | 0.84 | 1.20 |
| Remote consultation rate | 0.02 consults per person-month | All active patients (n=100) | Incidence rate ratio | 0.77 | 1.56 |
| Patient trust | 3.5 (sd=0.5) | Sampled patients (n=20) | Absolute effect | -0.07 | 0.07 |

A change in either consultation rate of an equivalent of one visit per person-year is considered “clinically significant”, which is well outside our minimum detectable range. Similarly, we will be able to identify reasonably small changes (~0.15 standard deviations) in patient trustworthiness score, although we do not hypothesise a change in this outcome.

Patient participant recruitment and sampling

At the study commencement each cluster provides the study with a pseudonymised list of active patients, giving us a patient ID and the basic information, we need from each patient (age, sex and eligible diagnosis). At the clinic they will have a link to patient ID with the patient’s record but we will not have access to the patient personal data. This is the open cohort for each cluster.

Each month we collect from each clinic a record of the consultations conducted and prescriptions and investigations ordered by the clinic, all they need to provide is the number of visits by type, prescriptions, investigations and any other information we need linked to a patient ID (e.g. patient 1234 had one remote visit, 2 prescriptions). Any additional patients can join the open cohort if they become eligible during the trial period.

Using the information, the research team can calculate outcomes, remove patients that are no longer active/who default, and sample for participation in the trust and patient activation outcomes and the process evaluation interviews. We will return the list of sampled patient identification number to the clinic for them to contact the potential participant so the research team can commence the informed consent processes.

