This method of recruitment and sampling limits the amount of information to be collected each month, enables the tracking of patients each month to maintain the open cohort within each clinic, it simplifies the sampling process, and maintains patient confidentiality.

[figure not shown]
The research participation response rate experienced by our partners range from 60-80% and we will sample 30 patients each month to achieve our target sample of 20 per month.

Methods: Assignment of interventions

A number of outcomes will be collected by interviewing a random sample of 20 patients who have received a consultation in the previous month. To reduce the transfer of patient identifiable data and their contact details, we specify the following sampling protocol. On the first calendar day of each month the list of patients who have had at least one consultation in the preceding month will be aggregated within each cluster site by the facility representative. The list will be pseudonymised by redacting identifiable information including patient name and contact details but keeping unique IDs, such as row numbers, and other basic data to permit comparisons between sampled and interviewed

groups for quality control. The list will be photographed and sent to the trial statistician, who will send back a random sample. Data collection from the selected patients can then proceed.

Figure 1: Cluster randomisation sequencing

Allocation

Within each country the 20 participating clusters will be randomised to one of ten sequences (see figure 1) with two per sequence. A random number will be generated for each cluster and then clusters assigned to each sequence in ascending order of the generated number. The randomisation will be conducted by the trial statistician who will be blinded to cluster name. The intervention implementers and clinics will not be blinded to allocation sequence as this is impractical given the need to plan and prepare training.

Blinding

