All models will be estimated using restricted maximum likelihood using the R package lme4. We will report point estimates, confidence intervals, and p-values but not make any claims of “statistical significance” given recent strong arguments against doing so[17]. P-values will be based on the null hypotheses $H_0: \delta = 0$ versus the two-sided alternatives $H_1: \delta \neq 0$ in each of the models. Given there are multiple primary outcomes we will adjust reported p-values for multiple testing using a stepdown method, which provides an efficient means of controlling the family-wise error rate[18]. We will derive the exact distributions of the test statistics to perform the stepdown procedure using a permutation test approach, by re-randomising clusters to different sequences in the stepped-wedge design[19]. This method ensures appropriate control of the family-wise error rate and avoids potential biases resulting from small numbers of clusters.

Data management

Each country team will store consent forms and raw data on their own university secure password protected server or if paper-based, such as consent forms, in a locked filing cabinet. The data will be electronic in an email attachment, or a photo of a list, or entered into a survey software, on the REaCH Moodle or a digital recording. The exact nature of the raw data will depend on the available infrastructures of individual clusters and their geographical proximity to the university. Data will be translated as necessary and transcribed locally. We will ensure a confidentiality agreement is in place for all transcribers. Two members of the local country team (one unblinded) will have access to a list which links a patient identifier to their identity and their informed consent forms. For REaCH trainees this will be three people because the facilitators will also know their identity and have access to their Moodle data. These will remain stored locally throughout the trial and not leave the country.

In Tanzania, data will be stored virtually in a server at Commission for Science and Technology (COSTECH) [name]. Email: [contact] Research Registry Office [contact]

Physical data will be stored at St. Francis University College of Health and Allied Sciences, Ifakara Health Institute (IHI), [name].

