| | Participant expresses distress during interview or survey. | Ask whether participant would like to pause or stop interview or survey. Offer discussion with their clinical team. Remind them of contact telephone number. |

Appendix 5. Changes to REaCH trial timelines (reported to King’s Ethics Committee on 20 August 2021)

As reported at the PMG dated 11.05.22, both trials were running behind our originally planned schedule. Following conformation of the UKRI/ODI funding restoration, [name], Principal Investigator, approached the funder to request a four-month time-only extension. They confirmed on 17.06.21 that they were unable to offer us an extension beyond the current financial year (related to the ODA funding issue) but they would be able to award the study a further five weeks. The trial must now complete by 31.03.22. The final report must be submitted by 30.06.22.

[figure not shown]
The Nigeria trial is on track to complete final data collection by mid February 2021 and so is able to continue as per current plan.

Nigeria as of June 2021

The Tanzania trial had a delayed start and without changes was currently due to complete in April 2022. We therefore needed to propose some amendments to the trial design.

Tanzania as of June 2021

[figure not shown]

REaCH study proposal to complete both trials by 31.03.22

We proposed to continue the Nigeria trial as per protocol.

We propose to revert the Tanzania trial to the earlier discussion we had when first threatened with loss of funding. This proposal was to reduce the trial length by reducing the sequences and increasing the number of clusters trained in each sequence. We propose six sequences of three or four clusters per sequence.

Tanzania New timeline

Impact on the power of the trial

The trial has a mixture of superiority and non-inferiority inferential goals. As such we originally considered the “minimum detectable effect size” the trial would provide with a power of 80%, type I error rate of 5%, intraclass correlation coefficient (ICC) of 0.05, and cluster autocorrelation coefficient of 0.8. The table below presents the revised power calculation for the Tanzania trial.

| Outcome | Baseline assumed | Denominator population | Treatment effect | Original design | | Proposed re-design | |
|---|---|-----------------------------|----------------------|---------------------------------|---------------------------------|---------------------------------|---------------------------------|

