| | | | | Lower minimum detectable effect | Upper minimum detectable effect | Lower minimum detectable effect | Upper minimum detectable effect |
| Face to face consultation /prescription rate | 0.25 consults/ prescriptions per person-month | All active patients (n=100) | Incidence rate ratio | 0.84 | 1.20 | 0.81 | 1.23 |
| Remote consultation rate | 0.02 consults per person-month | All active patients (n=100) | Incidence rate ratio | 0.73 | 1.38 | 0.69 | 1.45 |
| Patient trust | 3.5 (sd=0.5) | Sampled patients (n=20) | Absolute effect | -0.07 | 0.07 | -0.08 | 0.08 |

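### The remote-consultation minimum detectable effect differs between the sample-size table and Appendix 5, and the pair 0.77/1.56 cannot come from one calculation

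*Protocol*

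**What the plan says.** The Sample size section of the Protocol justifies trial size by minimum detectable effects instead of power for a target effect. It bases them on the statistical models given later and on "a power of 80%, a type I error rate of 5%, an ICC of 0.05, and a CAC of 0.8". For the remote rate (baseline 0.02 per person-month) the table row reads "All active patients (n=100) | Incidence rate ratio | 0.77 | 1.56". The face-to-face/prescription row gives 0.84/1.20 at a baseline of 0.25. The trust row gives ±0.07 with SD 0.5 and 20 sampled patients.

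Appendix 5 (Impact on the power of the trial) repeats the calculation for the original design and adds the shortened Tanzania design. Its stated inputs are "power of 80%, type I error rate of 5%, intraclass correlation coefficient (ICC) of 0.05, and cluster autocorrelation coefficient of 0.8". Its remote row reads "Incidence rate ratio | 0.73 | 1.38 | 0.69 | 1.45": the first two figures are the original design and the last two the six-sequence re-design. Its original-design figures for face-to-face and trust are identical to those in the Sample size table.

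On the design, the Protocol says "We plan to recruit 20 clusters in each country for the trial", with clusters "randomised to one of ten sequences (see figure 1) with two per sequence". Under Inference, tests are set against the null "versus the two-sided alternatives", and "Given there are multiple primary outcomes we will adjust reported p-values for multiple testing using a stepdown method". The Outcomes section names four primary outcomes.

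**The concern.** Two different answers are printed for one calculation. The mismatch is not a superseded figure, because the Appendix 5 columns restate the original design with the same inputs and only the remote row differs. Read across the two tables, the shorter six-sequence Tanzania design (upper bound 1.45) looks more precise for an increase than the full ten-sequence design (1.56).

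The minimum detectable effects are the protocol's only quantitative case for the size of the trial, and the remote rate is the outcome on which an increase is hypothesised. A reader cannot tell from the document what precision to expect on it. Separately, the table's 5% error rate is not the level at which the four primary p-values will be reported.

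**Working it through.** **Symmetry of the printed pairs.** With a log link and one standard error, both bounds equal exp(±k·SE), with k = 1.960 + 0.842 = 2.802. The logs of the printed pairs are:

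| Pair | ln lower | ln upper | Ratio of sizes (upper/lower) |
|---|---|---|---|
| 0.84 / 1.20 | -0.174 | +0.182 | 1.05 |
| 0.73 / 1.38 | -0.315 | +0.322 | 1.02 |
| 0.81 / 1.23 | -0.211 | +0.207 | 0.98 |
| 0.69 / 1.45 | -0.371 | +0.372 | 1.00 |
| 0.77 / 1.56 | -0.261 | +0.445 | 1.70 |

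The last pair implies SE = 0.261/2.802 = 0.093 from one bound and 0.445/2.802 = 0.159 from the other. If 1.56 is right, power at 0.77 is Φ(0.261/0.159 - 1.960) ≈ 0.38. Evaluating the Poisson variance at the alternative does not explain this: a lower rate gives fewer events, so the lower bound should lie further from 1 on the log scale, not closer.

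**Reproducing the other rows.** Inputs from the Protocol are 20 clusters, ten sequences of two, 100 patients per cluster-month, ICC 0.05, CAC 0.8 and two-sided 5%. Two things are assumed. The first is 11 to 13 monthly periods: the sequence figure is not shown, and Participant timeline gives twelve data months. The second is month fixed effects. The method is generalised least squares on the log scale, with sampling variance 1/(100 × rate) per cluster-month and cluster variance τ² split 0.8/0.2 between cluster and cluster-month.

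- Face-to-face: taking ICC = τ²/(τ² + 1/rate) gives τ² = (0.05/0.95) × (1/0.25) = 0.2105. The result is 0.83–0.84 / 1.19–1.20 (stated 0.84/1.20).
- Trust: sampling variance is 0.25 × 0.95/20. The result is 0.072–0.076 (stated 0.07). At a type I error of 0.0125 it would be 0.086–0.090, so the table was set at an unadjusted 5%.

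**The same model for the remote rate.** Sampling variance is 1/(100 × 0.02) = 0.5.

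| Between-cluster variance | Month effects | Lower | Upper |
|---|---|---|---|
| τ² = 0.2105 (face-to-face value) | yes | 0.64–0.65 | 1.54–1.56 |
| ICC 0.05 on the remote rate, τ² = (0.05/0.95) × 50 = 2.63 | yes | 0.52–0.54 | 1.86–1.93 |
| none | yes | 0.71 | 1.41 |
| τ² = 0.2105, 11 periods | no | 0.731 | 1.368 |
| none, 11–12 periods | no | 0.766–0.774 | 1.31–1.29 |

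The no-clustering limit with month effects can be checked by hand. Over 11 months the treated fraction p runs 0, 0.1, …, 1, so the sum of 20p(1-p) is 33. Then SE = √(0.5/33) = 0.123, 2.802 × 0.123 = 0.345, and exp(±0.345) = 0.71/1.41. With the variance taken at the alternative it becomes 0.68/1.38, so 1.38 is met there but 0.73 is not.

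None of the variants gives 0.77 together with 1.56. The pair 0.73/1.38 is approached only by dropping month effects, and the face-to-face row then becomes about 0.88/1.13, against the stated 0.84/1.20.

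**Multiplicity.** At 0.05/4 = 0.0125 the two-sided critical value is 2.498. Power at an effect sized for 80% at 5% is Φ(2.802 - 2.498) ≈ 0.62. Detectable effects grow by (2.498 + 0.842)/2.802 = 1.192: face-to-face to 0.81/1.24 and trust to ±0.083.

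**Clinical benchmark.** One visit per person-year is 1/12 = 0.083 per month. That is an IRR of 1 ± 0.083/0.25 = 0.67/1.33 for face-to-face and 1 + 0.083/0.02 ≈ 5.2 for an increase in remote visits.

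**The case against.** Several stronger readings are tempting, and the documents do not support them.

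- *0.77 and 0.73 are unattainable.* This holds only with month effects. The linear predictor printed under Statistical methods shows no explicit time term, and without one and without clustering 0.77 can be reached. It then pairs with about 1.3, not 1.56. Likewise 0.73/1.38 is not impossible; it is inconsistent with the rows beside it.
- *The right pair is 0.64/1.56.* That figure carries the face-to-face log variance to a rate of 0.02. Under the same formula the remote ICC would be 0.2105/(0.2105 + 50) ≈ 0.004, not the stated 0.05. No single replacement can be fixed from the text.
- *The Tanzania remote row (0.69/1.45) is tighter than any design allows.* With monthly steps the no-clustering limit is 0.64/1.56, but with two-month steps it is 0.73/1.37, inside the stated range. The new timeline is a figure not shown.
- *Precision for the hypothesised increase is not delivered.* On one defensible calculation the upper bound is 1.56, exactly as the Sample size table states. The bound out of line would then be the lower one.
- *The adjusted tests have 62% power.* That is a Bonferroni bound. The planned permutation stepdown can use correlation between outcomes and relaxes after each rejection. The Protocol also disclaims claims of significance and offers these effects as a guide to precision.

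What stands against all of this is the contradiction between the tables, the impossible asymmetry, and the unstated difference between planning and reporting error rates.

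**Conclusion.** The remote row of the Sample size table is wrong as written. It contradicts Appendix 5 under identical inputs, and its two bounds imply standard errors of 0.093 and 0.159 for the same design. This needs no modelling assumption beyond a common standard error on the log scale, which all the other rate-ratio pairs respect.

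That Appendix 5's 0.73/1.38 is not a safe replacement rests on the assumptions that reproduce the face-to-face and trust rows: month effects and 11 to 13 periods. Under those, the remote effect lies between about 0.64–0.65/1.54–1.56 and 0.52–0.54/1.86–1.93, according to the ICC scale.

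The multiplicity mismatch is real but secondary: at worst 62% power and effects 19% larger on the log or absolute scale, and less under the planned stepdown. The claim about one visit per person-year survives, since 0.81/1.24 lies inside 0.67/1.33 and even 1.93 is far below 5.2.

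**What to change.** 1. Recompute the remote row once with the model used for the other rows. State the scale on which the ICC of 0.05 applies to count outcomes, whether period effects are included, and the number of periods.
2. Print the same pair in the Sample size table and in the original-design columns of Appendix 5. Do not simply copy 0.73/1.38 across. If the ICC scale is uncertain, show the pair for each scale.
3. Recompute the Tanzania re-design remote row on its actual step schedule.
4. Add one sentence saying that the minimum detectable effects are per comparison at an unadjusted 5%, that reported p-values are family-wise adjusted over four primary outcomes, and that the Bonferroni worst case is about 62% power or effects up to 19% larger.

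The cost is one recalculation and a few lines of text. Design, data collection and analysis do not change. The remote figures may look less favourable, and the clinical-significance statement can stay.

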The evaluation consists of two stepped-wedge cluster randomised trials running concurrently in Nigeria and Tanzania. The REaCH intervention will be rolled out to all clusters over the course of the trial in a staggered fashion and the order that clusters receive the intervention will be randomised. The evaluation will comprise both the quantitative trial outcomes and a process evaluation. The

evaluation in each country will be conducted independently; comparisons between results will be predominantly qualitative. As a secondary analysis we will estimate the between country difference in treatment effects, although the trials are not designed for this purpose.

Methods: Participants, interventions, and outcomes

Study setting

We propose two identical trials in contrasting countries with marginalised populations: 1) Rural/remote, low income Tanzania in East Africa and 2) Urban and peri-urban in middle income Nigeria in West Africa.

Participants

Health workers and patients receiving healthcare from participating primary care facilities. Tier 1 trainees are doctors/nurses/ medical officers who speak, read and write in English, tier 2 are other cadres e.g. community health workers, pharmacy assistants, receptionists etc who may communicate in English or in local languages. The tier 1 and tier 2 trainees work as a team within the facility.

Eligibility criteria

Primary care facilities

Recruited primary care facilities will individually, or in collaboration with other smaller facilities, become a research cluster. We will recruit 20 clusters which must have 1) a minimum of 100 active patients with one of the eligible long-term conditions attending for healthcare three times per year. Active patients are those for whom there is record of a consultation within the previous five months. 2) paper-based or electronic record keeping of patient names, phone number, age, sex, appointments attended and with whom and pharmacy/investigation records 3) employ a minimum of five health workers. At least one must be tier 1 with the remainder a mix of tier 1 and 2 providing healthcare to citizens 4) Facility managers consent to all parts of the study including process evaluation.

Health workers

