Primary care facilities will be in the study for 14 months. Month 1 to recruit and set up training and procedures on trial methods and pilot data collection methods and data quality assurance methods. Months 2-13 to provide pseudonymised open cohort data and support REaCH training and patient

recruitment. Month 14 will be for the collection of missing data, final data quality checks and closing the trial site down.

Health workers will be in the trial for between one and six months depending upon when they receive REaCH training and whether they take part in the process evaluation.

Patient participants will remain in the trial for the time it takes to complete two questionnaires which we estimate to be less than 60 minutes. If they offer consent to be interviewed they will remain in the study for a further six weeks from the point of conducting the survey to give sufficient time for the sampling framework to be consulted and an interview to be set up and completed.

Interventions

Experimental Intervention: REaCH training is designed to increase the use and quality of remote consulting [7] that meets ethical and professional regulation standards. Our definition of remote consulting is when a person with a perceived health need consults a healthcare provider using a mobile phone [3,5]. They will use the internet or telecommunications infrastructure and will use SMART phones or feature phones to communicate. Our LMIC definition includes consultations using non-mobile technology (e.g. a computer in a community centre or a shared fixed telephone line in a remote rural village).

REaCH training uses a blended learning Moodle app and cascade process which support the delivery of trustworthy, safe and scalable remote primary healthcare [7]. REaCH trainees are doctors/nurses/medical officers who work for primary healthcare facilities in Tanzania and Nigeria (tier 1 trainees). They subsequently cascade training in local languages to five health workers in their team (tier 2 trainees). Tier 1 training consists of 20 hours of self-directed learning plus local tutor/peer time over 2/3 weeks using a smart phone. Tier 2 training is cascaded remotely via feature phone or through locally established team meetings/training with prescribed social distancing. REaCH is informed by the TRAIN framework for optimising sustainability of changes in healthcare delivery following a cascaded learning process in LMIC [9].

REaCH curriculum

| Module | Learning Outcome |
|--|---|

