In each local trial delivery team, one investigator and 1 research assistant will remain blinded to the month during which REaCH training was delivered to each cluster. Each facility is given a unique identification number consisting of 4 digits. We use four digits to make it more difficult for the research team to recall cluster IDs when discussing with the unblinded education team. This will reduce bias when monthly data collection is undertaken. When education and research teams meet together, clusters will be referred to by identification number only. At the beginning of every data collection activity the researcher will remind the health worker or patient participant not to reveal whether the facility has undertaken REaCH training. Data entry will be undertaken by a database assistant who will be blinded to whether the data is from a cluster in the intervention or the control. At the bi-weekly trial team meetings we will have an agenda item to check with every blinded member whether they think they have been unblinded in relation the identity of a randomised cluster during the previous two weeks. All UK investigators will be blind to cluster randomisation except the Birmingham trial statistician.

Methods: Data collection, management, and analysis

Trial data collection methods

At trial set up each cluster will provide the research team with a pseudonymised whole facility population of eligible patients. This is the open cohort. On the same day/date of every month the clinic will provide the research team with four lists:

- 1) A list of pseudonymised patients who had face to face consultations since the last data period
- 2) A list of pseudonymised patients who had remote consultations since the last data period
- 3) A list of pseudonymised patients who had prescriptions ordered and collected since the last data period
- 4) A list of pseudonymised patients who had investigations ordered since the last data period

From the combined monthly lists of 1 and 2, the research team will generate a random order list of 30 pseudonymised patients to sample for completion of the patient reported outcome data. Once informed consent procedures are completed, the researcher will undertake a structured interview with the participant by telephone to complete the two questionnaires.

Table 1: Complete listing of the trial data collected

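### At the protocol's own rates, about 24 to 27 patients per cluster-month can be surveyed, so a draw of 30 is not available on average and the n=20 behind the trust precision is optimistic

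*Protocol*

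**What the plan says.** Four elements of the protocol bear on the size of the trust survey.

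- **Cohort size.** Sample size: "we expect there to be an average of 100 active eligible patients at any one time in each cluster". Eligibility criteria, Primary care facilities, also makes this figure a floor: "a minimum of 100 active patients with one of the eligible long-term conditions attending for healthcare three times per year".
- **Consultation rates.** The Sample size table assumes "0.25 consults/prescriptions per person-month" face to face and "0.02 consults per person-month" remotely.
- **Sampling frame and draw.** Patient participant informed consent, Methods: Assignment of interventions, and Trial data collection methods all restrict the survey to patients with at least one consultation in the month. From the combined face-to-face and remote lists, "the research team will generate a random order list of 30 pseudonymised patients".
- **Target.** Patient participant recruitment and sampling quotes partner response rates of 60-80% and says "we will sample 30 patients each month to achieve our target sample of 20 per month". The trust row of the Sample size table, with a stated MDE of ±0.07, is based on 20 sampled patients.

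Participant timeline in the trial adds: "Patient participants will remain in the trial for the time it takes to complete two questionnaires". The protocol gives no rule for months when the list is shorter than 30, and it does not say whether someone already surveyed may be drawn again.

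**The concern.** The draw of 30 and the consultation rates come from the same plan but do not fit together. The list is limited to people who consulted that month, and its expected length follows from cohort size and rates. If it is usually shorter than 30, the yield of 20 is not supported.

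Trust is a primary outcome, and the protocol uses its MDE to show how strong the evidence on superiority or non-inferiority can be. That figure should rest on a number of surveys the design can be expected to produce. Separately, the implied total of surveys per cluster exceeds the cohort size, so whether patients may take part more than once needs to be stated.

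**Working it through.** **Inputs from the protocol.** 100 active patients per cluster; rates 0.25 and 0.02 per person-month; response 60-80%; trust SD 0.5; ICC 0.05; CAC 0.8; power 80%; two-sided 5%; 20 clusters in 10 sequences of two; 12 data months (months 2-13).

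**Assumptions.** SD 0.5 is the total SD. Period effects are fixed. Visits are either independent Poisson with a common rate (the protocol's count model is Poisson) or spaced so that nobody consults twice in a month.

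**Step 1: reproduce the stated MDE.** Variance components are cluster 0.05 × 0.8 × 0.25 = 0.010, cluster-period 0.05 × 0.2 × 0.25 = 0.0025, and residual 0.95 × 0.25 = 0.2375. The covariance of a cluster's 12 period means is 0.010 in every cell, plus 0.0025 + 0.2375/n on the diagonal. The generalised least squares standard error of the treatment effect at n=20 is 0.0263. MDE = (1.96 + 0.84) × 0.0263 = 0.074, which agrees with the stated 0.07. With 13 periods it is 0.072. The stated figure is correct for n=20.

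**Step 2: patients available to sample.** Consultations per cluster-month: 100 × (0.25 + 0.02) = 27.

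- No repeat visits: 27 patients.
- Poisson visits: 100 × (1 − e^−0.27) = 23.7 patients. The chance that a month's list reaches 30 is about 9%.

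The mean list is below 30 under either assumption.

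**Step 3: completed surveys and MDE (12 periods).**

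| Visits | Response | Completed surveys | Trust MDE |
|---|---|---|---|
| Poisson | 60% | 23.7 × 0.6 = 14.2 | 0.0845 |
| Poisson | 80% | 23.7 × 0.8 = 18.9 | 0.0754 |
| No repeats | 60% | 27 × 0.6 = 16.2 | 0.080 |
| No repeats | 80% | 27 × 0.8 = 21.6 | 0.072 |
| As planned | – | 20 | 0.0738 |

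The largest loss is 0.0845/0.0738 = 1.145, or about 15%. In SD units, that is 0.15 rising to 0.17.

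**Step 4: what a mean of 20 would need.** With no repeat visits, response must be 20/27 = 74%. Under Poisson visits it must be 20/23.7 = 84%, above the quoted range. Alternatively, under Poisson visits, the cohort must be 20/(0.8 × 0.2366) = 106 patients at 80% response or 20/(0.6 × 0.2366) = 141 at 60%.

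**Step 5: repeat participation.** The target is 20 × 12 = 240 surveys per cluster from a cohort averaging 100. Even 14 a month gives 168. Repeats follow unless cohort turnover is very large.

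**The case against.** Much can be said for the plan. Long-term-condition visits three times a year are likely to be spaced, so 27 may be nearer the truth than 24. At 74% response or more, inside the quoted range, 20 is then reached. The figure of 100 is also the eligibility floor, so recruited clusters may well be larger. Drawing 30 to obtain 20 implies 67% response, which is reasonable in itself. When the list has 24-27 names, a draw of 30 in practice means approaching everyone. The precision loss is small, the protocol already accepts an MDE of 0.08 for the Tanzania redesign, and it sets no numerical trust margin that 0.08 would breach.

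All of this stands, and it limits the point to a planning figure that sits towards the favourable end. It does not remove it: the Sample size section plans on an average of 100, and at that size the list falls short of 30 on average whichever visit pattern is assumed.

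Three stronger readings are tempting but not supported.

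- *The target of 20 is unattainable.* It is attainable with spaced visits and good response, or with larger clusters.
- *Each patient may be surveyed once only*, giving 60-80 surveys per cluster, 5-7 a month and an MDE of 0.115-0.130. The timeline sentence describes how long two questionnaires take; it does not bar re-sampling. Statistical methods treats months as repeated cross-sections because patients are hard to link over time, which allows for recurrence. The cohort is also open, not a fixed 100.
- *Control months will be thinner than intervention months.* This holds only if total consultations rise after training. The background text speaks of remote consultations replacing face-to-face ones, and then the list need not grow.

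**Conclusion.** The point holds as a fault of internal consistency with a modest effect. At 100 active patients and baseline rates, the list averages about 24-27, so the planned draw of 30 is not available on average. The expected yield is about 14-22 completed surveys per cluster-month: 14-19 under Poisson visits, 16-22 with no same-month repeats. Most of that range lies below 20. The trust MDE is then about 0.072-0.085, against 0.074 at n=20.

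These figures rest on clusters of exactly 100, the protocol's own rates and response range, 12 analysed periods and a total SD of 0.5. Larger clusters, or more consultations after training, would ease the shortfall. The conclusion is not that the trust analysis lacks adequate precision, but that the n behind its stated precision is optimistic.

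**What to change.** 1. In Patient participant informed consent, Patient participant recruitment and sampling, and Trial data collection methods, replace the fixed draw of 30 with an invitation to all eligible patients who consulted in the month, up to 30. Draw at random only when the list is longer. Align the sampling text under Methods: Assignment of interventions.
2. In Sample size, restate the expected completed surveys as about 14-22 per cluster-month, assuming clusters of 100, and the trust MDE as about 0.07-0.085. If clusters are expected to be larger, give the size and recompute.
3. In Appendix 5, recheck the Tanzania trust MDE of ±0.08 over the same range, since it also takes n=20. The revised timeline is in a figure missing from the text reviewed, so no replacement value is offered here.
4. State that a patient may be surveyed in more than one month, and align the participant timeline with this.

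The cost is a slightly less favourable stated precision and some rewording. No interviews are needed beyond those already planned.
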